- **iv. Power**
- Sample Size: Each of the 4 sites will recruit 38 infants (total $N=152$) to retain 35 infants for a total of $N = 140$ infants in the study. The initial ($N=152$) and retained ($N=140$, $n=70$ per condition) sample sizes were chosen according to feasibility of recruitment in each site as well as considerations of time and resources needed for a 4-year study.
- Power analysis for Primary Hypotheses 1 & 2: We used a simulation-based power analysis (Muthén & Muthén, 2002; Theommes et al, 2010) to estimate the power for the randomized trial with repeated measures design as evaluated with the proposed Linear mixed modeling (LMM; Laird & Ware, 1982; Wallace & Green, 2002) utilizing FIML for attrition-based missing data. *Mplus* was used for simulations and empirical analyses. Simulations were based on detecting significance in the treatment by time interaction during the intervention phase, γ_{11} . The analysis assumed a small intraclass correlation for the slope across infants (e.g., small variance of the treatment effect of 0.05; Raudenbush & Liu, 2000), a two-tailed nominal error rate of $\alpha = .05$, an initial sample size of 152 infants at baseline, and an attrition scenario of 10% loss by the end of the 3-month intervention (based on patterns observed in previous research conducted by the collaborative team). We conducted the power analysis essentially in support of Hypothesis 1 (the short-term effect at the end of the intervention phase) based on the position that Hypothesis 2 will be supported if the initial effect is then at least sustained through the follow-up period which would be evidenced by a non-significant γ_{21} parameter (no differential change). Prior published research by [name] et al. (2010) and Heathcock et al. (2008) were used to derive effect size estimates for sitting (GMFM, $d=1.21$) and reaching (toy contacts, $d=1.32$), respectively. Pilot data from [name] & [name] and [name] were used to derive

effect size estimates for global development (Bayley III, $d=0.43$) and problem solving (IGDI, $d=1.11$), respectively.

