- Based on our previously stated assumptions and the cited pilot data and prior research, power analyses suggest that the targeted sample size will be sufficient to detect the reported effects with greater than 80% power for three of the four primary outcomes. With $N=152$ initial participants, power to detect mean group differences in slopes during the intervention period is >99% for sitting, 93% for reaching, and >99% for problem solving. As these three outcomes are estimated to be over-powered based on pilot/cited data, given the projected initial sample size of $N=152$ we would be able to detect effect sizes as small as $d=0.48$ for sitting, $d=0.66$ for reaching, and $d=0.56$ for problem solving. Based on the effect size derived from pilot data, power to detect mean group differences in global development improvement during the intervention period at the $d=0.43$ level is only 48%; however, given the projected sample size, we would be able to detect an effect size of $d=0.64$ with 80% power.
- *Power analysis for Primary Hypotheses 3 & 4:* Continuing to use the variability and mean differences from the cited prior research and pilot data as estimates of paths A and D in Figure 2, we conducted an empirical power analysis based on the SEM model presented in Figure 2 using an initial sample size of $N = 152$ infants, and assuming a moderate correlation between the measures at baseline ($r = .32$, explained variance = 10%). With these assumptions, we will have 80% power to be able to support the hypotheses of partial mediation of intervention-driven change over time in global development by intervention-driven changes in sitting and reaching and problem solving if the standardized parameter estimate of the mediator(s) on change in global development (paths B (Hyp. 3) or $C_1 * C_2$ (Hyp. 4) in Figure 2) is at least $\beta=.237$, which corresponds to a medium effect.

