- A complementary power analysis perspective for evaluating Hypotheses 3 and 4 follows MacCallum et al.'s (1996) guidelines for determining adequacy to test the fit of a model, which indicates whether the necessary parameters/effects are being considered. Evaluation of model fit is a prerequisite for evaluating parameters within the model itself. Accordingly, a hypothesis of *close model fit* can be tested by assuming the Type I error rate to be 0.05, a $RMSEA \leq 0.05$ as indicative of *close fit*, and a $RMSEA > 0.10$ as indicative of poor fit. Given the proposed model in Hypothesis 3, $df_{min}=51$, $N=152$, $RMSEA_{null}=0.05$, $RMSEA_{alt}=0.10$, and $\alpha=0.05$, the power to detect close model fit for Hypothesis 3 is >.99. Given the proposed model in Hypothesis 4, $df_{min}=115$, $N=152$, $RMSEA_{null}=0.05$, $RMSEA_{alt}=0.10$, and $\alpha=0.05$, the power to detect close model fit for Hypothesis 4 is .96.
- In summary, the initial sample size of $N=152$ and retained sample size of $N=140$ (70 per group) is appropriate for the study and will likely yield power to test each primary hypothesis at a medium effect size or larger at the $p < .05$ level, with a power of at least .80. The structure of this proposal ensures that we can realistically produce the first randomized efficacy trial of sitting and reaching with young infants within the funding period.

v. Measures [Outcomes]

Rationale for using multiple measures of developmental skills

The use of standardized tests in isolation is not optimal for infants with neuromotor disorders because of the large increments of change in observable motor skills needed to change the score on any one item, and the complexity of child behavior. Furthermore, our research has shown that standardized assessments like the Bayley III focusing on the discrete performance of tasks are not consistent for identifying and classifying delays in the first two years of life and are poorer predictors of future cognition relative to assessments that involve perceptual-motor

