such as Bayley score at baseline by adding additional parameters to this portion of the model. A random intercept (u_{0i}) and random slopes ($u_{1i}RX_{it}$ and $u_{2i}LT_{it}$) will be included to capture individual differences in outcome levels at entry into the study, and change through each phase of the study (intervention and follow-up). Finally, we will include a residual term (ε_{it}). We expect that γ_{01} , the mean difference between conditions at baseline, will not differ significantly from zero, reflecting no initial group differences and an effective randomization. This parameter also serves to statistically control for any differences at baseline (significant or otherwise) that may be observed despite the random assignment to condition. The parameter, γ_{11} , as the difference between condition slopes through the end of the intervention, is expected to be significantly greater than zero, reflecting a larger rate of change in outcomes as a result of START-Play participation; and γ_{21} as the difference between condition slopes during follow-up will either be not significantly different from zero, reflecting maintenance of the net intervention effect, or significantly greater than zero, reflecting a continued improvement in outcomes due to the START-Play intervention. Estimates of effect sizes with confidence intervals will be provided.

[figure not shown]
Control of the family-wise error rate (FWER) is necessitated by the presence of multiple outcome measures as discussed in the prior **rationale for using multiple measures of developmental skills**. We define the family of tests as containing the four primary outcomes as described in the Measures section. We will control FWER by conducting the permutation step-down procedure (Westfall & Young, 1993) within a repeated measures design (Lix & Sajobi, 2010) allowing for estimation of intervention effects while controlling for correlation between outcomes due to the common theory of change construct.

Evaluation of Primary Hypotheses 3 & 4:

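### The stated detectable effects are unadjusted .05 figures for outcomes that will be tested with a family-wise step-down, so 80% power at those effects is not assured

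*SAP*

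**What the plan says.** **Power (SAP section iv, Primary Hypotheses 1 & 2).** The simulation targets "detecting significance in the treatment by time interaction during the intervention phase", with "an initial sample size of 152 infants at baseline", 10% loss by month 3, and "a two-tailed nominal error rate of" .05. Each outcome is handled separately.

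- Planning effects: d=1.21 sitting, 1.32 reaching, 1.11 problem solving, 0.43 Bayley III.
- Stated power at those effects: above 99%, 93%, above 99% and 48%.
- For the first three the SAP adds that "we would be able to detect effect sizes as small as" d=0.48, 0.66 and 0.56. For Bayley it gives d=0.64 with 80% power. Only the Bayley value carries an explicit 80%; for the others it is implied by context.

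**Summary (end of section iv).** The sample size "will likely yield power to test each primary hypothesis at a medium effect size or larger at the" .05 level, with power of at least .80.

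**Multiplicity (section ix, after the LMM).** The family is the four primary outcomes: "We will control FWER by conducting the permutation step-down procedure", citing Westfall and Young. Section iv mentions neither the family nor an adjusted threshold, and the multiplicity paragraph does not return to power.

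**The concern.** A step-down over four outcomes starts at a stricter threshold than .05. It relaxes to .05 for an outcome only after the other three have been rejected. The detectable effects were computed as if every outcome were always judged at .05. They are offered to show that N=152 copes with effects smaller than the pilot values, and that is the situation in which the other outcomes are least certain to reject and the step-down costs most.

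At stake is how a null result on one outcome is read. Someone relying on section iv would conclude that an effect of the stated size had an 80% chance of being found, when the chance under the planned test could be up to 18 points lower.

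**Working it through.** **Inputs.** From the SAP: two-sided .05, the detectable and planning effects above, and a family of four. Assumed: one test per outcome, approximately normal test statistics, and a common correlation of 0 to 0.8 among them. The SAP gives no such correlation; its r=.32 is a baseline correlation between measures for the mediation model. Variance components are not reported, so each standard error (SE) is back-solved as SE = d/(1.960 + 0.842) = d/2.802.

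**1. Reproduce the plan's figure.** Bayley: SE = 0.64/2.802 = 0.228. Power at 0.43 = Φ(0.43/0.228 − 1.960) = 46.9%, against 48% stated. The same back-solve at .025 gives 43%, and at .0125 gives 40%. The stated pair fits an unadjusted .05.

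**2. First-step level.** Bonferroni over four tests: .05/4 = .0125, critical value 2.498.
- Power at a stated detectable effect: Φ(2.802 − 2.498) = 62%.
- Detectable effect multiplier: (2.498 + 0.842)/2.802 = 1.19, giving 0.57/0.79/0.67/0.76 (sitting/reaching/problem solving/Bayley).

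**3. Full step-down.** A max-T step-down on four correlated normals stands in for the permutation version (400,000 draws per scenario). Critical values for 4, 3, 2 and 1 remaining outcomes at r=.32 are 2.47, 2.37, 2.23 and 1.96.

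| True effects | Power, correlation 0 to 0.8 |
|---|---|
| All four at stated detectable values | 72–74% each |
| Only one outcome affected, at its detectable value | 62–68% |
| Sitting, reaching or problem solving at its detectable value, others at planning effects | 74–75% |
| Bayley 0.64, others at planning effects | about 80% |
| Bayley 0.43, others at planning effects | about 47% |

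The last three rows take reaching's SE from d=0.66. If it is taken from the stated 93% instead, they become 73–75%, 79% and 46–47%.

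Hand check of the third row at zero correlation: sitting and Bayley are effectively the last two outcomes, with threshold 2.238. Sitting clears it with probability Φ(2.802 − 2.238) = 71.4%. A further 80.0 − 71.4 = 8.6% falls between 1.960 and 2.238 and counts only if Bayley has rejected, with probability Φ(1.882 − 2.238) = 36%. The total is 71.4 + 8.6 × 0.36 = 74.5%.

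**4. The medium-effect summary, at d=0.5.** Unadjusted power is Φ(0.5 × 2.802/d − 1.960), with d the stated detectable effect: 83/56/71/59% (sitting/reaching/problem solving/Bayley). Under the step-down at r=.32 it is about 72/46/59/48%. The step-down removes roughly 10 to 12 points; the rest of the shortfall is already there.

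**5. Reaching.** If d=0.66 has 80% power, SE = 0.236 and power at 1.32 is Φ(5.60 − 1.96), above 99.9%. If power at 1.32 is 93%, SE = 1.32/(1.960 + 1.476) = 0.384 and the detectable effect is 0.384 × 2.802 = 1.08. The two stated figures cannot both hold, so every reaching figure here that is built on 0.66 is conditional on it.

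**The case against.** The best defence is that a step-down is not Bonferroni: once the other outcomes reject, the last is tested at the full .05. This stands where the plan is most explicit. Bayley d=0.64, the one effect tied in words to 80%, keeps about 80% when the other three have their planning effects. At the planning effects generally, sitting and problem solving stay at or above 99%, reaching goes from 93% to about 90% on its less favourable figure, and Bayley stays near 47%, which the SAP already reports as low. The claim of more than 80% power for three of four outcomes at the planning effects therefore survives.

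The defence does not rescue the other three detectable effects. Bayley has under 50% power at its planning effect, so it often has not rejected, and sitting, reaching or problem solving at its detectable value then faces the two-outcome threshold.

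It is also fair that the SAP openly calls its error rate nominal, that the Bayley pair is arithmetically sound, and that section iv says N was chosen on feasibility and resources. This is a mismatch between the planning assumption and the planned test, not a calculation error.

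**Conclusion.** The point holds in a limited form. The four detectable effects are marginal figures at an unadjusted .05, and under the planned step-down 80% power at those values is not assured. The loss ranges from almost nothing (Bayley, others at planning effects) through 5–8 points to 12–18 points (only one outcome affected). These sizes rest on back-solved SEs, a normal max-T stand-in for the permutation procedure and an assumed correlation. The correlation matters little within each scenario; the true effects on the other outcomes matter more.

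Three stronger readings are not supported:
- That the stated effects never have 80% power. The Bayley case above contradicts this.
- That multiplicity explains why the medium-effect summary fails. At d=0.5 three of four outcomes miss .80 with no adjustment at all, as the SAP's own detectable effects of 0.66, 0.56 and 0.64 imply.
- That the sample size must rise or the error control is faulty. N was set by feasibility, and the step-down already addresses type I error. Only the power statement is out of line.

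**What to change.** Re-run the existing simulation with the planned step-down over the four outcomes and a stated range of correlations. Report power and 80% detectable effects for three scenarios: all outcomes affected, one affected, and the planning effects. Reconcile the two reaching figures (93% at d=1.32, detectable d=0.66) before quoting either. Reword the end of section iv so that it no longer claims power of at least .80 for each primary hypothesis at a medium effect. N, data collection and the analysis method stay as they are. The cost is a simulation re-run and less favourable stated figures.

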- c. problem-solving Variable: IGDI problem-solving score
- d. global development Variable: Bayley III score

Hypothesis 2: Compared to the BAU group, the START-Play group will show greater sustained improvements from pre-intervention to one year since start of intervention (long-term effect) in:

- a. sitting Variable: Gross Motor Function Measure (GMFM) sitting scores
- b. reaching Variable: Number of toy contacts
- c. problem-solving Variable: IGDI problem-solving score
- d. global development Variable: Bayley III score

Hypothesis 3 (Mediation): Improvements in global development will be (at least) partially mediated by improvements in problem-solving as a function of the intervention at the end of the project (long-term proximal effect).

Variables: GMFM scores, toy contacts, IGDI problem-solving and Bayley III scores.

SECONDARY HYPOTHESES

Analysis of moderators

1. *Hypothesis:* Severity of motor impairment will have a significant influence on overall change in IGDI problem-solving, and motor scores, as well as Bayley III scores. Variable: Severity score (see Table 1)

2. *Hypothesis:* Factors external to the child (socialization opportunities [Modified Parent Child Interaction-Dyadic Mini Code scores (Censullo, 1991) (PCI-DMC)], and home environment (HOME Inventory [Bradley, 1993] & SES), will have a moderate effect on change in GMFM, problem-solving, and Bayley III scores.

Further analysis of motor variables

3. *Hypothesis:* The START-Play group will show posture control measures that are closer to normative values than the BAU group from pre to post intervention. This hypothesis tests additional variables quantifying sitting to supplement Primary Hypothesis 1. Variables: Kinematic measures taken from video analysis.

4. *Hypothesis:* Compared to the BAU group, the START-Play Intervention group will show greater improvements in duration of toy contact and object manipulation from pre to post intervention. This hypothesis tests additional variables quantifying reaching to supplement the

Primary Hypothesis 2. Variables: Unilateral and bilateral contact number and duration, and type of contact (i.e. hand open or closed; palmar or dorsal hand surface, manipulation variables).

iii. Research Design

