Evaluation of Primary Hypotheses 1& 2. A piecewise LMM with repeated measures will be used to simultaneously address the primary research hypotheses: (1) compared to the BAU group, the START-Play group will show greater improvements in sitting, reaching, problem-solving and global development from pre- to post-intervention (short term effect); and (2) compared to the Business as Usual (BAU) group, the START-Play group will show greater sustained improvements from pre-intervention through one year since the start of intervention (long-term effect). The effects of interest will be the child-level *time by group* (START-Play vs. BAU) interaction evaluated at (a) the end of the third month (Hypothesis 1 - after completion of the intervention period), and (b) the long-term follow-up phase through kindergarten (Hypothesis 2). Tested simultaneously, these interactions will indicate whether the change in outcomes due to participation in the START-Play intervention condition differs significantly from any change in outcomes that occur with BAU. Primary outcome measures (GMFM) sitting scores, toy contacts, IGDI (problem solving), Bayley III) will be analyzed separately so all measures can be clearly

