assessed for the full potential of information. Appropriate error-rate control is discussed in a later section. Severity of neuromotor disorder (stratification variable) and fidelity of implementation will be added as covariates, and child-level characteristics, such as gender and ethnicity, also may be included in the analysis as child-level covariates. Due to the small sample size ($J = 4$) and the convenience sampling of sites involved in the study, site will be included as a *fixed* classroom level effect rather than an additional hierarchical level or random effect. Our analytic model is presented as a piecewise LMM where Y_{it} is the outcome variable score at time t for child i , TRT_{0i} is a contrast variable denoting the intervention status for child i (i.e., 0=BAU, 1=START-Play), RX_{it} is the passage of time during the intervention phase of the study from baseline to the end of the third month, and LT_{it} is the passage of time from the end of intervention through one calendar year since entering the study. While presented here as linear effects within each study phase (RX and LT), we will also explore any potential curvilinearity as well. The second line of the equation reflects the remaining fixed covariate effects ($CTRL_{0i}$ =neuromotor disorder severity, fidelity;

COV_{0i} =child covariate [i.e., gender]; and S_{0i} =site). *The model can be expanded to consider additional covariates*

$$Y_{it} = \gamma_{00} + \gamma_{01}TRT_{0i} + \gamma_{10}RX_{it} + \gamma_{20}LT_{it} + \gamma_{11}TRT_{0i}RX_{it} + \gamma_{21}TRT_{0i}LT_{it} + \gamma_{02}CTRL_{0i} + \gamma_{03}COV_{0i} + \gamma_{04}S_{0i} + u_{0i} + u_{1i}RX_{it} + u_{2i}LT_{it} + \varepsilon_{it}$$

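### Hypothesis 2 claims a benefit at 12 months, but the SAP judges it by a non-significant follow-up slope difference and never tests the 12-month difference

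*SAP*

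**What the plan says.** SAP section ii words Hypothesis 2 as "greater sustained improvements from pre-intervention to one year since start of intervention (long-term effect"), for GMFM sitting, toy contacts, IGDI problem-solving and Bayley III.

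Section ix fits a piecewise linear mixed model. RX counts time over the 3-month intervention. LT "is the passage of time from the end of intervention through one calendar year since entering the study", which is nine months. γ₁₁ is the group difference in the RX slope and γ₂₁ the group difference in the LT slope.

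Two places say how Hypothesis 2 will be judged:

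- Section iv (power for Primary Hypotheses 1 and 2) makes support depend on whether "the initial effect is then at least sustained through the follow-up period which would be evidenced by a non-significant" estimate of γ₂₁.
- Section ix (Primary Hypotheses 1 and 2): γ₂₁ "will either be not significantly different from zero, reflecting maintenance of the net intervention effect", or else will be significantly positive, which is read as continued improvement.

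Section ix also names, as the effect of interest, the group-by-time interaction for "the long-term follow-up phase through kindergarten (Hypothesis 2"). It says the interactions are tested simultaneously and promises effect sizes with confidence intervals, without naming the contrast.

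The power simulation addressed γ₁₁ only: "power to detect mean group differences in slopes during the intervention period is >99% for sitting, 93% for reaching, and >99% for problem solving". Bayley III has 48% power at d=0.43 and 80% at d=0.64. The section nevertheless concludes that the sample size "will likely yield power to test each primary hypothesis at a medium effect size or larger", with power of at least .80.

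**The concern.** With RX running 3 months and LT running 9, the group difference in change from baseline to month 12 is 3γ₁₁ + 9γ₂₁. Neither document names or tests that quantity. The SAP asks instead for an initial effect plus a γ₂₁ that is not significantly negative. That creates two problems.

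- **A lost benefit can pass.** Non-significance may only mean that the follow-up slope is poorly estimated. Imprecision confined to follow-up, such as dropout after month 3, makes the rule easier to satisfy after a fade.
- **A real benefit can fail.** An effect that shrinks but is still present at month 12 can make γ₂₁ significantly negative. That is neither of the supporting outcomes in section ix, and the SAP does not say how it would be reported.

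Fading is a realistic scenario. Section 2 of the protocol cites a review in preterm infants where early cognitive gains were gone by school age. Bayley III, the primary measure of global development, is the most exposed because it has the weakest power.

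**Working it through.** **1. Reproduce the plan's figure.** Normal approximation, two-sided α=0.05. From the SAP's 80% power at d=0.64, the standard error of the 3-month Bayley III difference is 0.64/(1.960+0.842) = 0.228. Power at d=0.43 is then Φ(0.43/0.2284 − 1.96) = Φ(−0.08) = 46.9%, against 48% stated. The two Bayley III figures agree.

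**2. Assumptions for follow-up.** The documents give no standard error for the follow-up change and no correlation between the two phase estimates. I take:

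- 3γ₁₁ and 9γ₂₁ estimates bivariate normal, with standard errors s₁ and s₂
- s₂/s₁ = 1.0 or 1.3 (also 1.5 and 2.0)
- correlation ρ = −0.5, −0.42 or −0.23
- no step-down adjustment

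**3. Bayley III benefit wholly lost by month 12.** The mean of 3γ₁₁ is +0.43 and that of 9γ₂₁ is −0.43, so the true 12-month difference is zero. Support under the SAP's rule is P(Z₁ > 1.96 and Z₂ > −1.96), with Z₁ centred at 0.43/s₁ and Z₂ at −0.43/s₂.

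| s₂/s₁ | Support, SAP rule | Among trials passing the 3-month test (divide by 46.9%) | Support, direct contrast |
|---|---|---|---|
| 1.0 | 16.6-21.2% | 35-45% | 2.5% |
| 1.3 | 25.4-29.4% | 54-63% | 2.5% |
| 2.0 | 35-37% | 74-80% | 2.5% |

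A wider check derived s₂/s₁ and ρ by generalised least squares for the section ix model:

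- visits at 0, 3, 6 and 12 months; N=152; 10% lost by month 3 and a further 0, 10 or 20% later
- intercept variance 1; residual variance 0.1 to 0.5; SD of true 3-month change 0.2 to 1.0
- monthly follow-up slope SD one third or 0.6 of the intervention-phase slope SD
- results rescaled to the standard error in step 1

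It gave ratios of 1.0-2.0 and false support of 20-39%.

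**4. No effect in either phase.** The same rule declares support in 2.0-2.3% of trials. The problem arises only when a real early effect fades.

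**5. Fewer infants overall.** Raising both standard errors 1.3-fold (ρ=−0.5) lowers the Bayley III rate from 16.6% to 14.4%, because the 3-month test fails more often. Only imprecision specific to follow-up makes things worse.

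**6. Other outcomes, full fade from the planned effects.** I take the detectable effects as 80%-power values, which the SAP states explicitly only for Bayley III. Standard errors are then 0.48/2.802 = 0.171 (sitting), 0.66/2.802 = 0.236 (reaching) and 0.56/2.802 = 0.200 (IGDI). False support is at most 0.02% at ratio 1.0 and about 1% at 1.3. Over the wider grid it reaches 6% for sitting and 21% for reaching and IGDI.

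Reaching is less secure. Its 93% power at d=1.32 implies a standard error of 1.32/(1.960+1.476) = 0.384, not 0.236; with 0.384 the rates are 5-6% (ratio 1.0) and 20-22% (ratio 1.3).

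**7. The opposite error.** Let sitting fall from d=1.21 to 0.73, a loss of 0.48 with a real benefit remaining.

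| s₂/s₁ | γ₂₁ significantly negative | Power of the 12-month contrast |
|---|---|---|
| 1.0 | 80% | 93-99% |
| 1.3 | 58% | 84-95% |
| 1.5 | 46% | 76-90% |
| 2.0 | 29% | 56-69% |

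**8. Power of the direct contrast if Bayley III d=0.43 is fully sustained.** Its standard error is √(s₁² + s₂² + 2ρs₁s₂): 0.228 to 0.283 at ratio 1.0 and 0.269 to 0.330 at 1.3. Power is Φ(0.43/SE − 1.96): 33-47% and 26-36%. Over the wider grid it is 14-41%.

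**The case against.** The best defence has five parts.

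- **Status of the rule.** The power-section sentence mainly justifies simulating γ₁₁ alone, and section ix states what γ₂₁ is expected to show. But section ix does interpret non-significance as maintenance. Testing two slopes simultaneously is not testing their weighted sum, and the promised effect sizes are not tied to a 12-month contrast or to the decision.
- **The word sustained.** On this reading, a significantly negative γ₂₁ properly counts against Hypothesis 2, so the sitting example is no error. That is a fair reading. It also shows that the direct contrast alone would not establish full retention. It does not rescue the use of non-significance as evidence of retention, which would need a margin.
- **How often.** The unconditional Bayley III rates of 17-29% are moderate. The larger share, 35-63%, applies among trials that have already passed at month 3. Both are far above 2.5%.
- **Anchoring.** The wide variance grid is only loosely tied to the SAP's slope variance of 0.05. Reading 0.05 as a 3-month variance gives about 20-30%, and as a monthly variance about 21-37%. The 39% upper end should carry little weight. The step-down adjustment is left out throughout.
- **Scope.** At the planned effects, a complete fade in sitting, reaching or IGDI would usually be detected. This stands, with the reservation about reaching.

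**Conclusion.** The concern holds. Hypothesis 2 is stated as a 12-month difference and judged by something else, and absence of a significant slope difference is read as persistence. That conclusion follows from the text and needs no assumption.

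The numerical exposure lies mainly with Bayley III: false support is some 7 to 12 times the 2.5% of a direct test (16.6/2.5 = 6.6; 29.4/2.5 = 11.8) for standard error ratios of 1.0 to 1.3. Those rates assume a complete fade from d=0.43, approximate normality, and the ratios and correlations listed. The claim of at least .80 power for each primary hypothesis has no basis for Hypothesis 2, since no power was computed for γ₂₁ or for the 12-month difference. Because the hypothesis is primary and the repair uses the model already planned, it should be made before analysis.

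**What to change.** - In section ix, define the Hypothesis 2 test for each primary outcome as 3γ₁₁ + 9γ₂₁, or as the model-based 12-month difference in change if curvilinear terms are used. Report it with a confidence interval and adjust it across the four outcomes by the planned step-down procedure.
- Report γ₂₁ with its confidence interval as description only. Remove the statements in sections iv and ix that non-significance shows maintenance.
- If retention itself is to be claimed, prespecify a retention margin; the contrast shows only that a benefit exists at month 12.
- Give Hypothesis 2 its own power calculation in section iv, with stated follow-up variance and attrition after month 3, and revise the summary power claim.
- Correct the reference to kindergarten in section ix to 12 months. This is a wording slip, since LT already ends at one year.

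The cost is SAP wording, one linear contrast per outcome carried through the permutation procedure, and a rerun of the power simulation. No new data are needed. The price is openly lower power for Bayley III at 12 months than the current text implies.

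### For reaching, 93% power at d=1.32 and a detectable effect of d=0.66 cannot both hold at N=152, and the two close-fit powers are reversed relative to their degrees of freedom

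*SAP*

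**What the plan says.** SAP section iv (Power) bases the power analysis for primary Hypotheses 1 and 2 on simulation of the treatment-by-time slope during the intervention phase. It uses a two-sided 5% level, 152 infants at baseline and 10% loss by month 3. The planning effects are d=1.21 for sitting, 1.32 for reaching (toy contacts), 1.11 for problem solving (IGDI) and 0.43 for global development (Bayley III).

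Power at the first three is ">99% for sitting, 93% for reaching, and >99% for problem solving". The section calls these outcomes over-powered and gives the smallest detectable effects at the same N as 0.48, 0.66 and 0.56 respectively. For Bayley III, power "during the intervention period at the $d=0.43$ level is only 48" per cent, but "we would be able to detect an effect size of $d=0.64$ with 80% power". That is the only detectable effect printed with its power level.

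For the mediation models, the section sets N=152, alpha 0.05, and RMSEA 0.05 against 0.10. With a minimum df of 51, "the power to detect close model fit for Hypothesis 3 is >.99". With a minimum df of 115, "the power to detect close model fit for Hypothesis 4 is .96". The closing summary says the sample size "will likely yield power to test each primary hypothesis at a medium effect size or larger", with power of at least .80.

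Protocol section 5 (Sample selection and size) reports a power range of 93% to 99% for N=152.

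**The concern.** Once N, the model and the variance inputs are fixed, power at one effect size determines power at every other. Doubling the effect from 0.66 to 1.32 should take power from a conventional 80% to almost 100%, not to 93%.

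The SAP's own neighbouring figures point the same way. The planning effect divided by the detectable effect is 1.11/0.56 = 1.98 for problem solving and 1.32/0.66 = 2.00 for reaching. If both detectable effects are set at the same power level, reaching should have at least as much power as problem solving. It is printed with less.

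Toy contacts is one of four primary outcomes, and SAP section v says the power analysis was based on it. How a null reaching result should be read depends on whether the trial could detect 0.66 or only about 1.08. If 93% is right, the claim for 0.66 fails, and so does the summary's .80 power at a medium effect or larger for this outcome.

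The close-fit pairs raise a similar question. With N, alpha and both RMSEA values fixed, power rises with the degrees of freedom, yet the larger model is printed with the lower power.

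**Working it through.** **Inputs.** All come from SAP section iv: two-sided alpha 0.05, N=152, and the planning effects, powers and detectable effects listed above.

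**Assumptions.** One standard error (SE) per outcome, and 80% power for every detectable effect. The SAP prints 80% only for Bayley III. The variance inputs are not all given, so absolute power cannot be rebuilt; what can be checked is whether each pair of figures agrees.

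**Formulas.**
- Power at d = Φ(d/SE − 1.960)
- Detectable effect at 80% power = (1.960 + 0.842) × SE = 2.802 × SE

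**Check on the other outcomes.**
- Bayley III: SE = 0.64/2.802 = 0.2284. Power at 0.43 = Φ(0.43/0.2284 − 1.960) = 46.9%, against 48% printed. In reverse, 48% at 0.43 implies a detectable effect of 0.63, against 0.64 printed.
- Sitting: SE = 0.48/2.802 = 0.1713. Power at 1.21 is above 99.9%, consistent with >99%.
- Problem solving: SE = 0.56/2.802 = 0.1999. Power at 1.11 = 99.98%, consistent with >99%.

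Bayley III is the only sharp check. A printed >99% is easily met: any detectable effect up to 0.791 for sitting or 0.726 for problem solving would give at least 99%.

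**Reaching, starting from 0.66.** SE = 0.66/2.802 = 0.2356. Power at 1.32 = Φ(1.32/0.2356 − 1.960) = 99.99%, against 93% printed.

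**Reaching, starting from 93%.** SE = 1.32/(1.960 + 1.476) = 0.3842. Detectable effect = 2.802 × 0.3842 = 1.08, against 0.66 printed. Power at 0.66 = Φ(0.66/0.3842 − 1.960) = 40%.

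**Sensitivity.**

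| Variation | Result |
|---|---|
| 93% is a rounding of 92.5% to 93.5% | Detectable effect 1.09 to 1.06; power at 0.66 is 40% to 41% |
| Noncentral t, 138 df | Unchanged: 99.99%, 1.08, 40% |
| One-sided alpha 0.05 | Power at 1.32 = 99.96% |
| 0.66 taken at 90% power | Power at 1.32 above 99.99% |
| 0.66 taken at only 50% power | Power at 1.32 = Φ(2 × 1.960 − 1.960) = 97.5% |
| Power at 1.32 required to be at least 99% | Detectable effect must be 0.86 or less |

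None of these produces the printed pair. With one SE, it requires 0.66 to be the effect detectable at about 40% power. Keeping 80% at 0.66 requires an SE 0.3842/0.2356 = 1.63 times larger in the run at 1.32.

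**Close fit.** The statistic is noncentral chi-square with noncentrality (N − 1) × df × RMSEA², and N − 1 = 151.

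| df | Noncentrality, RMSEA 0.05 | Noncentrality, RMSEA 0.10 | 5% critical value | Power | Printed |
|---|---|---|---|---|---|
| 51 | 19.25 | 77.01 | 93.56 | 0.965 | >.99 |
| 115 | 43.41 | 173.65 | 192.78 | 0.9998 | .96 |

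At N=140 the powers are 0.947 and 0.999, in the same order. The printed values agree with the calculation once they are exchanged.

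**The case against.** The best defence is that the closed form is not the SAP's method. The SAP simulated a slope contrast in a mixed model with attrition, and took its effect sizes from other studies whose variances it does not report. If 1.32 and 0.66 were scaled to different standard deviations, or a variance input changed between runs, one SE would not link them. The 80% level for 0.66 is also an inference. Both points stand as conditions on the result. They do not rescue the figures, because the SAP describes no such change and the same formula comes within about one percentage point of the Bayley III power.

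A second objection is that nothing turns on the discrepancy. Section iv says N was chosen on feasibility, time and resources, and 93% at the planning effect already exceeds 80%. That is right about the design and about the over-powered label. It does not settle which effect the trial can detect.

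Third, the closing summary is doubtful whichever reaching figure is right. If medium means d=0.5, which the SAP does not say, then detectable effects of 0.66, 0.64 and 0.56 correspond to 56%, 59% and 71% power at 0.5. The summary is also hedged, and the SAP openly reports 48% for Bayley III. This is fair: the reaching discrepancy is not the only reason to qualify the summary.

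Finally, the Protocol's omission of 48% is selective reporting rather than an arithmetic error. It is kept here only because the same Protocol sentence carries the disputed 93%.

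**Conclusion.** The concern holds. Given one SE per outcome and 80% power for the detectable effect, the two reaching figures cannot both be true. The detectable effect is either 0.66 or about 1.08, a 1.6-fold difference (1.08/0.66), and rounding does not explain it. The value 0.66 lies near the other detectable effects (0.48, 0.56, 0.64), whereas 93% is repeated in the Protocol. Neither observation settles which is wrong. This does not show that the trial is underpowered at its planning effect for reaching.

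The close-fit reversal rests only on printed inputs and needs no such assumptions. Whether the powers or the df values were exchanged cannot be told from the documents. Both powers exceed .80 either way, so this part is a reporting error only.

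The correction should be made, because it concerns a primary outcome and the fix is cheap.

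**What to change.** 1. Check or re-run the toy-contacts simulation. Print power at d=1.32 and the detectable effect as a matching pair, with the power level stated. Stating that level for sitting and problem solving as well would remove the ambiguity.
2. If 0.66 is confirmed, change power at 1.32 to >99%. If 93% is confirmed, change the detectable effect to about 1.08 and qualify the section iv summary for reaching.
3. In either case, say what a medium effect means in that summary and check the claim against all four detectable effects.
4. Correct the 93% to 99% range in Protocol section 5 to match the result, and add the 48% for Bayley III.
5. Confirm the df of each mediation model, then correct the close-fit pairs. Settle the hypothesis numbering first: SAP section ii lists three primary hypotheses, with mediation as the third, while sections iv and ix refer to Hypotheses 3 and 4, and section ix makes mediation by problem solving the fourth.

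The cost is one simulation to check or re-run, two df values to confirm, and text corrections in both documents. Sample size and design are unaffected.
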